4.1 Study Endpoints

4.1.1 Efficacy Endpoints

The SDI, completed by the caregiver as proxy for the subject, will be performed according to the Schedule of Procedures and Assessments.

4.1.2 Safety Endpoints

Subjects will have routine safety assessments during the Extension Phase, including monitoring, questioning and recording of AEs, measurements for ECGs, vital signs, and weight, and blood and urine collection for clinical hematology and chemistry analysis, urinalysis, and the eC-SSRS.

4.2 Study Subjects

4.2.1 Definitions of Analysis Sets

Safety Analysis Set: the group of Extension Phase subjects who received at least 1 dose of Treatment Phase study drug and had at least 1 postdose safety assessment

4.2.2 Subject Disposition

The number of subjects entered in the Extension Phase and the number of subjects completing the Extension Phase will be presented. Subjects who prematurely terminated their participation in this extension phase will be summarized by their primary reason for study termination. Other reasons for study drug and study terminations will also be summarized. These tabulations will be produced for all subjects by modal dose.

4.2.3 Protocol Deviations

Protocol deviations, as specified by the monitor, will be categorized into major and minor deviations prior to unblinding and will be listed. Major protocol deviations will be summarized by modal dose group.

4.2.4 Demographic and Other Baseline Characteristics

Demographic and other baseline characteristics for the Safety Analysis Set will be summarized by modal dose using descriptive statistics. Continuous demographic and baseline variables include age, height, and weight; body mass index (BMI); categorical variables include sex, age group (60 to <65 , 65 to <75 , 75 to <85 , and 85 to 90), BMI group (<18.5 , 18.5 to <25 , 25 to ≤ 30 , and >30 kg/m², or other suitable categorization), race, ethnicity, and country.

4.2.5 Prior and Concomitant Therapy

All investigator terms for medications recorded in the eCRF will be coded to an 11-digit code using the World Health Organization Drug Dictionary (WHO DD) (Mar 2016 or latest version). The number (percentage) of subjects who take prior and concomitant medications will be summarized on the Safety Analysis Set by modal dose group, Anatomical Therapeutic Chemical class (ATC), and WHO DD -preferred term (PT).

Prior medications are defined as medications that stopped before the first dose of Extension Phase study drug.

Concomitant medications are defined as medications that (1) started before the first Extension Phase dose of study drug and continued at the time of the first dose of study drug, or (2) started on or after the date of the first Extension Phase dose of study drug to the last dose day plus 14 days. All medications will be presented in subject data listings.

4.2.6 Treatment Compliance

Compliance will be summarized by visit as reported by investigators.

Compliance for lemborexant will also be calculated on the basis of the number of tablets dispensed, lost, and returned as (total number of tablets dispensed – total number of tablets returned – total number of tablets lost)/total of number of tablets should have been taken.

Summaries will provide descriptive summary statistics and number (percentage) of subjects below 80%, between 80% and 120%, and greater than 120%.

4.3 Efficacy Analyses

SDI will be summarized by visit and modal dose based on the Safety Analysis Set.

4.4 Safety Analyses

Safety analyses will be performed on the Safety Analysis Set. Safety data, presented by modal dose group, will be summarized on an “as treated” basis using descriptive statistics (eg, n, mean, standard deviation, median, minimum, maximum for continuous variables; n [%] for categorical variables). Safety variables include treatment-emergent adverse events (TEAEs), clinical laboratory parameters, vital signs, 12-lead ECG results, eC-SSRS. Study Day 1 for all safety analyses is defined as the date of the first dose of study drug in the Core Study.

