2.2 Overall Study Design and Plan

2.2.1 Extension Phase

The Extension Phase comprises a 30-month Maintenance Period (Treatment Period) and a 14-day Follow-Up Period.

Subjects who complete the Core Study End of Study (EOS) Visit within 30 days prior to enrollment in the Extension Phase will be eligible for participation.

For subjects continuing directly from the Core Study to the Extension Phase, the End of Study (EOS) Visit of the Core Study will be the start of the Extension Phase.

Subjects who complete the Core Study, but who do not elect to immediately roll over to the Extension Phase will be required to return to the site within 30 days of completion of the Core Study and repeat selected assessments before being dispensed drug for the Extension Phase. If subjects return before 30 days of the last study visit, the tests that are required at that time are vital signs, weight, the Sleep Disorders Inventory (SDI), and the electronic Columbia-Suicide Severity Rating Scale (eC-SSRS). All other data will be carried over from Visit 6A. If subjects return on Day 30, all tests listed for Visit 6B will be performed. Details are as in (Figure 1).

During the Treatment Period, all subjects initially will receive lemborexant 10 mg per day (LEM10). At the discretion of the investigator, subjects will have the option of increasing the dose to lemborexant 15 mg per day (LEM15) or decreasing to lemborexant 5 mg per day (LEM5). All dose adjustments will be performed at an unscheduled visit or at the next scheduled visit.

All doses will be taken orally in tablet form each night for the duration of the Extension Phase immediately (ie, within 5 minutes) before the time the subject intends to sleep. The dose can be adjusted more than once during the Extension Phase. Subjects will receive 1 or 2 tablets as described below:

- LEM5: one lemborexant 5-mg tablet
- LEM10: one lemborexant 10-mg tablet
- LEM15: one lemborexant 5-mg tablet and one lemborexant 10-mg tablet

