Study visits, either in person or by telephone, will be conducted according to the Schedule of Procedures and Assessments for the Extension Phase. If the phone visit indicates an ongoing adverse event (AE), the subject should be brought to the clinic for an Unscheduled Visit. Subjects may discontinue from study drug for any reason. A subject who prematurely discontinues taking study drug should return to the clinic within 2 weeks of discontinuation to complete an Early Termination (ET) Visit. The assessments of the ET Visit are the same as those for the EOS Visit for the Core Study.

If the subject discontinues from the study due to an AE, the subject must complete an ET Visit, and the AE must be followed to resolution for a period of 4 weeks, whichever comes sooner.

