2.2.2 Follow-Up Period

The Follow-Up Period will be 14 to 18 days in duration and begins when subjects leave the clinic at the end of the Maintenance Period. Subjects and caregivers will return to the clinic at least 14 days but no more than 18 days after the end of the Maintenance Period for the End of Study Visit, including the recording of AEs and concomitant medications, and assessment of clinical laboratory tests, vital signs, and weight, and measurement of an electrocardiogram (ECG).

Treatment in the Extension Phase will last for a maximum duration of 30 months or until the lemborexant clinical development program for Irregular Sleep-Wake Rhythm Disorder (ISWRD) is discontinued. A study design that includes the Extension Phase is presented in [Figure 1](#).

[figure not shown]

Figure 1 Study Design

Note: Visit -1 is an optional Prescreening Period for subjects and caregivers who are unsure whether the subject has Irregular Sleep-Wake Rhythm Disorder (ISWRD). Subjects will wear an activity tracker for approximately 4 days, then return to the site to have the data from the activity tracker downloaded and analyzed to determine whether they are candidates for the study. (revised per Amendment 05)

Note: Visit 2 is a caregiver visit for downloading actigraphy data to determine eligibility; Visit 3 is the baseline visit for both subject and caregiver; Visit 4 is a visit for both subject and caregiver to download actigraphy data and perform safety assessments; Visit 5 is the end-of-treatment assessments visit; and Visit 6A is for end-of-study assessments for the Core Study. For subjects continuing directly from the Core Study into the Extension Phase, Visit 6A will be the start of the Extension Phase. Subjects who complete the Core Study, but who do not elect to immediately continue into the Extension Phase have up to 30 days after Visit 6A to participate. These subjects will be required to repeat selected assessments (Visit 6B) before being dispensed drug for the Extension Phase. Some subjects will have fewer visits based on the availability of lemborexant commercially.

ISWRD = Irregular Sleep-Wake Rhythm Disorder, V = Visit.

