7.1.4 Visit Window

All efficacy and safety data will be presented using derived visits as follows.

Visit	Target Visit Day (in study days)	Visit Window (in study days)
Ext. Visit 6B		On or prior to the study day of first dose of Extension Phase
Ext. Visit 7	73	Post study day of first dose of Extension Phase - 88
Ext. Visit 8	103	89-118
Ext. Visit 9	133	119-148
Ext. Visit 10	163	149-178
Ext. Visit 11	193	179-208
Ext. Visit 12	223	209-238
Ext. Visit 13	253	239-268
Ext. Visit 14	283	269-298
Ext. Visit 15	313	299-328
..etc	X	(X -14, X+15)

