8 PROGRAMMING SPECIFICATIONS

All efficacy and safety data will be presented using derived visit window described in this SAP. The rules for programming derivations and dataset specifications are provided in separate documents.

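### Extension visit windows run from the first Core dose, so one visit label covers different lengths of Extension treatment for direct and late entrants

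*SAP*

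**What the plan says.** Section 4.4 of the SAP fixes the clock for safety data: "Study Day 1 for all safety analyses is defined as the date of the first dose of study drug in the Core Study". Section 7.1.4 gives target days and windows in study days and applies them broadly: "All efficacy and safety data will be presented using derived visits as follows". Section 8 repeats the commitment: "All efficacy and safety data will be presented using derived visit window described in this SAP".

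The table in 7.1.4 uses two anchors. Visit 6B is everything up to the day of the first Extension dose, and Visit 7 is "Post study day of first dose of Extension Phase - 88", so its lower edge moves with the subject and its upper edge does not. Visits 8 to 15 are fixed ranges from 89–118 to 299–328, and later visits follow target −14 to target +15.

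Entry to the Extension is not at a fixed time. Under section 2.2.1 (Extension Phase), direct roll-over subjects start at the Core end-of-study visit; the others "will be required to return to the site within 30 days of completion of the Core Study", and return on Day 30 is provided for. The note to Figure 1 says that subjects who "do not elect to immediately continue into the Extension Phase have up to 30 days after Visit 6A to participate".

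For efficacy, section 4.3 says that "SDI will be summarized by visit and modal dose based on the Safety Analysis Set". No separate day origin is given for SDI.

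**The concern.** The Extension has its own treatment start, and its objective is long-term safety and tolerability over 30 months. A by-visit table is naturally read as showing status after a given time on Extension treatment. With windows counted from the first Core dose, a late entrant's gap before Extension drug is dispensed counts toward the visit label. Under the same label, that subject has had less Extension treatment than a direct entrant.

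This differs from ordinary window width. Width scatters visits around a target; the gap shifts an identifiable subgroup in one direction. The summaries exposed are those made by visit: SDI (4.3), laboratory values (4.4.3), vital signs (4.4.4), the by-visit ECG tables (4.4.5) and eC-SSRS (4.4.6). The Core Study enrols only about 60 subjects, so cells split by visit and modal dose may be small enough for a few late entrants to matter.

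**Working it through.** **Inputs from the SAP.** Study Day 1 is the first Core dose (4.4). Targets are 73, 103, …, 313, with the window rule X − 14 to X + 15 (7.1.4). The entry gap g after Visit 6A is 0 for direct entrants and up to 30 days for the others (2.2.1 and the note to Figure 1).

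**Reproducing the table.** Targets are 30 days apart. For Visit 8, 103 − 14 = 89 and 103 + 15 = 118; for Visit 15, 313 − 14 = 299 and 313 + 15 = 328. All eight windows for Visits 8 to 15 reproduce. They are contiguous and 30 days wide, and the Visit 7 upper edge is 73 + 15 = 88.

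**Overlap in Extension days.** Take two subjects with Visit 6A on the same study day. Let s be the study day of the first Extension dose for the direct entrant and s + g for the late entrant. Extension day = study day − day of first Extension dose + 1. Visit 8 then covers Extension days 90 − s − g to 119 − s − g. Against g = 0:

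- days shared under the label = 30 − g
- days spanned under the label = 30 + g

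| Gap g (days) | Shared days of 30 | Span under one label |
|---|---|---|
| 0 | 30 | 30 |
| 10 | 20 | 40 |
| 16 | 14 | 46 |
| 30 | 0 | 60 |

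These figures hold for each of Visits 8 to 15 and for any s. They count calendar days in a window, not the share of visits mislabelled.

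**Relabelling at equal Extension time.** Comparing study day d (direct) with d + g (late) for d = 89 to 298, which is 210 days, the label differs on 210 × g/30 of them: 70 at g = 10, 112 at g = 16, 210 at g = 30. At g = 30, everything a direct entrant has on study day 59 or later (59 + 30 = 89) carries the next visit's label for the late entrant. Earlier assessments stay in Visit 7.

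**Illustration under assumptions.** The SAP states neither the direct-entry day nor the origin of the Extension schedule. Assume s = 43 (73 − 30) and visits every 30 days from the first Extension dose.

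- Visit 8 is Extension days 47–76 at g = 0 and 17–46 at g = 30. Visit 7 is days 2–46 and 2–16.
- The first scheduled visit falls on study day s + g + 30. It leaves Visit 7 when s + g + 30 > 88, that is g ≥ 59 − s. For s = 43 the threshold is 16 days; for s = 47 it is 12.
- With s = 43, gaps of 1–15 days leave every on-schedule visit correctly labelled. Gaps of 16–30 days move every on-schedule post-baseline visit one label later and leave Visit 7 without one.
- The maximum 30-day offset relative to target Extension time is 30/61 = 49% at Visit 8 (103 − 43 + 1 = 61), 30/271 = 11% at Visit 15 (313 − 43 + 1 = 271) and 30/913 = about 3% at month 30 (taken as 913 days).

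**The case against.** The strongest reply is that no scheduled visit has been shown to be mislabelled. Visits "will be conducted according to the Schedule of Procedures and Assessments for the Extension Phase", and that schedule is not in the SAP. If the protocol times Extension visits from the first Core dose, the fixed study-day targets match it and the windows do their job; asking for time since the first Extension dose would then be an improvement to reporting rather than the repair of an error. This stands as a condition. It does not remove the problem, because even correctly scheduled visits would mix Extension-treatment times under one label, and the SAP does not tell the reader so.

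Complete separation occurs only at the 30-day maximum. Under the illustrative assumptions, gaps up to 15 days mislabel no on-schedule visit. Both points are correct, although a 30-day gap is a permitted case. The one-directional shift also assumes equal Core duration; variation there could add to the gap or offset it. The percentages and the 12-to-16-day threshold rest on an assumed entry day and illustrate the effect without measuring it.

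Finally, the consequences are limited. There is no hypothesis testing. Baseline labelling, TEAE incidence, exposure and the laboratory shift tables from baseline to end of study are unaffected, and ECG shift tables by post-baseline year would hardly change. All of that stands, and it limits the weight of the point.

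**Conclusion.** The concern holds. As written, the windows place direct and late entrants under the same visit label at different times on Extension treatment. In Visits 8 to 15 the shared Extension days fall by one for each day of gap, from 30 to none at 30 days, and the span under one label can double from 30 to 60 days. This follows from the printed windows and needs only equal Core duration for the two subjects compared.

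Whether scheduled visits receive wrong labels depends on the protocol's Extension schedule. The core-based origin is explicit for safety data and inferred for SDI. The effect is largest at the first visits and small late in a 30-month period. The number of late entrants is not given and may be small, so the effect on the summaries cannot be computed. The change should be made, but no test or error rate depends on it.

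**What to change.** In section 7.1.4, state the day origin of the windows for SDI as well as for safety data, after checking it against the protocol's Extension visit schedule.

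- **If visits are timed from the first Extension dose:** define Extension Day 1 as the date of that dose and restate the windows in Extension days with the same −14/+15 widths, taking targets from the protocol. Only if the schedule is every 30 days from that dose would the targets be 31, 61, 91 and so on, with Visit 7 = days 2–46 and Visit 8 = days 47–76. Each label then covers the same Extension days whatever the gap.
- **If visits are timed from the first Core dose:** say so in 7.1.4 and report time since the first Extension dose alongside the by-visit summaries.

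The Core-based study day can be kept for other uses. The cost is SAP wording and one derived variable; no new data are needed.

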4.4.1 Extent of Exposure

The extent of exposure (mean daily dose, cumulative dose, duration of exposure) to study drug will be summarized descriptively for lemborexant by modal dose based on the Safety Analysis Set.

4.4.2 Adverse Events

The AE verbatim descriptions (investigator terms from the eCRF) will be classified into standardized medical terminology using the Medical Dictionary for Regulatory Activities (MedDRA). AEs will be coded to the MedDRA (Version 18.0 or higher) lower level term closest to the verbatim term. The linked MedDRA PT and primary system organ class (SOC) are also captured in the database.

A TEAE for Extension Phase is defined as an AE that emerges during Extension Phase treatment, having been absent during the interval between the end of the Core and before Extension Phase Baseline) or

- Reemerged during treatment, having been present at pretreatment (Baseline) but stopped before treatment, or
- Worsened in severity during treatment relative to the pretreatment state, when the AE is continuous.

Only those AEs that are treatment-emergent will be included in summary tables. All AEs, treatment-emergent or otherwise, will be presented in subject data listings. AEs will be classified as TEAEs up to 14 days after the last study treatment.

An overview of the TEAEs will be summarized by modal dose group, including the number and percentage of subjects who experience TEAEs, treatment-related TEAEs, severe TEAEs, TEAEs leading to death and discontinuation from study/study drug.

The incidence of TEAEs will be reported as the number (percentage) of subjects with TEAEs by SOC and PT. A subject will be counted only once within an SOC and PT, even if the subject experienced more than 1 TEAE within a specific SOC and PT. The number (percentage) of subjects with TEAEs will also be summarized by maximum severity (mild, moderate, or severe). The number (percentage) of non-serious TEAEs with an incidence of greater than 5% will be summarized.

The number (percentage) of subjects with TEAEs will also be summarized by relationship to study drug (Yes [related] and No [not related]). Treatment-related TEAEs include those events considered by the investigator to be related to study treatment.

The number (percentage) of subjects with TEAEs leading to death will be summarized by MedDRA SOC and PT for each modal dose. A subject data listing of all AEs leading to death will be provided.

The number (percentage) of subjects with treatment-emergent SAEs will be summarized by MedDRA SOC and PT for each modal dose. A subject data listing of all SAEs will be provided.

The number (percentage) of subjects with TEAEs leading to discontinuation from study drug, the number (percentage) of subjects with TEAEs leading to dose reduction, and The number (percentage) of subjects with TEAEs leading to dose interruption will be summarized by MedDRA SOC and PT and by modal dose. Subject data listings of all AEs leading to discontinuation, leading to dose reduction, and leading to dose interruption will be provided.

The number (percentage) of subjects with TEAEs of cataplexy that are characterized according to the customized MedDRA query PT as potential cataplexy-related events (Section 9.2.8 of the Protocol), or as seizure-related events will be summarized as deemed necessary. Adjudicated events may also be presented separately.

The following adverse event tables will be also summarized by dose at first AE onset: The number (percentage) of subjects with TEAE by MedDRA SOC and PT, the number (percentage) of subjects with TEAE summarized by PT sorted by decreasing frequency, and the summary of selected AEs. A flag for dose at first AE onset will be created, and this set of tables will be then produced accordingly by ONSET dosing group (5 mg, 10 mg, and 15 mg) within the modal dose.

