4 STATISTICAL METHODS

All descriptive statistics for continuous variables will be reported using mean, standard deviation (SD), median, minimum and maximum. Categorical variables will be summarized as number (percentage) of subjects.

There will be no hypothesis testings, and data will be only be summarized by timepoint and by modal dose received by the subject.

Modal dose will be calculated as follows:

If subject has one dose start date and no dose end date, then subject has been on initial10 mg dose, model dose = 10 mg.

If a subject has start dose date and only one end date, and a second dose start date; then subject has been on 10 mg dose till first end dose date, the number of days on 10 mg is calculated as follows: first end date - first start date +1 , and number of days on the new dose is calculated as: database snapshot date- second start date +1. The modal dose is the most frequent of these two numbers, ... and so on.

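### Serious and treatment-limiting adverse events are summarised by modal dose, and no named summary table identifies them by dose at onset

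*SAP*

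**What the plan says.** SAP 4.4.2 fixes the layout for the most important event classes. For serious events: "The number (percentage) of subjects with treatment-emergent SAEs will be summarized by MedDRA SOC and PT for each modal dose". TEAEs leading to death have the same layout. TEAEs leading to discontinuation of study drug, dose reduction or dose interruption "will be summarized by MedDRA SOC and PT and by modal dose". Severe TEAEs appear in an overview by modal-dose group. The sentence on maximum severity names no grouping, so the general rule in 4.4 (safety data by modal-dose group) applies to it.

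Section 4.4.2 then adds a second view: "The following adverse event tables will be also summarized by dose at first AE onset". The list has three entries: all TEAEs by SOC and PT, all TEAEs by PT in order of frequency, and a summary of selected AEs, a term the SAP does not define. The layout is nested: "this set of tables will be then produced accordingly by ONSET dosing group (5 mg, 10 mg, and 15 mg) within the modal dose".

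On dosing, 2.2.1 starts every subject on 10 mg, allows a move up to 15 mg or down to 5 mg, and adds: "The dose can be adjusted more than once during the Extension Phase". Section 4 takes as modal dose the one with the most days. Under 4.4.1, exposure "to study drug will be summarized descriptively for lemborexant by modal dose based on the Safety Analysis Set".

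**The concern.** Modal dose describes a subject's whole treatment course. Dose at onset describes one event. The two can differ whenever the dose changes, and an adverse event is one reason for changing it. If the subject stays on treatment after the change, days accrued after the event help to decide the column in which it is counted. For an event that leads to a lasting reduction the shift has a direction: towards the lower dose.

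The Extension Phase exists to describe the long-term safety of flexible dosing at 5, 10 and 15 mg (SAP 2.1), and section 5 says that interim results will support new drug applications. Section 4.4 also describes the modal-dose summaries as being on an as-treated basis, so a reader could take the column to be the dose on which the event arose. The SAP already plans an onset-dose view for TEAEs in general, but not for the classes where the dose at onset matters most.

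**Working it through.** The SAP gives no figure to reproduce here. The check is a match of tables to groupings, followed by the modal-dose day count.

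**Step 1. Grouping of each class (SAP 4.4 and 4.4.2).**

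| Event class | Grouping of its own summary | Identified in an onset-dose table? |
|---|---|---|
| SAEs | Modal dose | No |
| TEAEs leading to death | Modal dose | No |
| TEAEs leading to discontinuation, reduction or interruption | Modal dose | No |
| Severe TEAEs | Modal dose (overview; general rule in 4.4) | No |
| All TEAEs by SOC and PT | Modal dose | Yes, within modal dose |
| All TEAEs by PT | Modal dose (general rule in 4.4) | Yes, within modal dose |
| Selected AEs (undefined) | Modal dose (general rule in 4.4) | Yes, within modal dose |

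Events in the first four rows are also counted in the all-TEAE onset tables, but nothing there marks them as serious, fatal, severe or treatment-limiting.

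**Step 2. When an event on 10 mg is counted under 5 mg.** Inputs: 10 mg start and possible dose change (2.2.1); maximum treatment of 30 months (2.2.2); most days decides (section 4). Assumptions: one reduction from 10 mg to 5 mg, and 5 mg continued to the end.

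- Length of treatment: 30 × 365.25 / 12 = 913 days.
- Let *a* be the days on 10 mg. Modal dose is 5 mg if 913 − *a* > *a*, that is *a* < 456.5, so *a* ≤ 456.
- At *a* = 30: 30 against 883 days, modal dose 5 mg.
- At *a* = 456: 456 against 457 days, modal dose 5 mg, although 456/913 = 49.9% of the days were on 10 mg.
- At *a* = 457: 457 against 456 days, modal dose 10 mg.

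For a shorter course of *L* days the rule is *a* < *L*/2. With *L* = 365, for example, a reduction after 182 days or fewer gives 5 mg (182 against 183).

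**Step 3. Whether the planned flag would do.** The planned flag records the dose at first AE onset. Suppose a subject has a mild event on 10 mg and later, on 15 mg, a serious event with the same PT. The first onset carries 10 mg; the serious event arose on 15 mg. A flag for the first event of the class is therefore needed.

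**Step 4. Denominators.** Everyone starts on 10 mg, so nearly the whole Safety Analysis Set counts as ever treated at 10 mg. The 5 mg and 15 mg groups are subjects whose dose was changed, with different time at dose. Section 4.4.1 gives exposure by modal dose only, so the SAP plans neither the number of subjects nor the time at each dose actually taken.

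**The case against.** The strongest reply is that nothing here contradicts itself. The SAP tests no hypothesis, labels its columns as modal dose, and already adds an onset-dose view. Every treatment-emergent event of these classes is in the all-TEAE onset tables, and because a subject has one modal dose, those counts can be summed over modal groups. Dedicated listings are planned for deaths, SAEs and AEs leading to discontinuation, reduction or interruption, and all AEs are listed. The Core Study has about 60 subjects and only some can enter the Extension Phase, so reading rare events from listings is workable. A TEAE leading to dose reduction cannot have arisen on 5 mg, the lowest dose, so that entry in a 5 mg column reveals itself.

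Much of this stands. The gap is in summaries, not in data, and a reader who inferred that these events never appear by onset dose would be wrong. But the onset tables do not mark the classes, and the SAP does not say that the listings will show dose at onset. The self-revealing argument covers only reductions in a 5 mg column. It does not cover an SAE or severe TEAE on 10 mg that was followed by a reduction, nor a reduction from 15 mg counted under 10 mg. Selected AEs and the separate table shells may overlap with these classes, but the SAP does not commit to that.

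The reply is also right that crude percentages of subjects ever treated at each dose would invite a misleading comparison, and that new flags are needed.

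**Conclusion.** The point holds as a cheap improvement. As written, the plan can place serious and treatment-limiting events under a dose other than the one on which they arose, and no named summary corrects this for those classes. In the simplest case (one reduction, 5 mg continued over a full 30 months) an event on 10 mg is counted under 5 mg whenever 10 mg lasted 456 of 913 days or less. That is a bound on one subject's course, not an estimate for the trial: the SAP gives no frequency or timing of dose changes, so the number of misplaced events is unknown.

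Two stronger readings are not supported.

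- A reader might infer that a large share of treatment-ending events after an increase to 15 mg would be counted under 10 mg. That depends on how days are counted for a subject who stops on the second dose, a case that section 4 does not write out, and on assumed risks and switch times.
- A reader might infer that onset-dose tables would also stop modal groups from changing between an interim and the final report. They would not. For an ongoing second dose, section 4 says that the "number of days on the new dose is calculated as: database snapshot date- second start date +1", so the retained modal-dose columns can still move with the snapshot. That is a separate issue.

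**What to change.** 1. In 4.4.2, add summaries by dose at onset, pooled over modal-dose groups, for SAEs, TEAEs leading to death, severe TEAEs, and TEAEs leading to discontinuation, dose reduction or interruption.
2. Define a class-specific flag: dose at onset of the first event of that class within each PT. For onset within 14 days after stopping, use the last dose taken.
3. Present these summaries mainly as counts. In 4.4.1, add the number of subjects ever treated and the subject-time at each dose actually taken, so that counts are read against exposure and not as crude percentages.
4. Keep the modal-dose tables, and state in 4.4 that their columns do not show the dose at onset.

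The cost is a few sentences, some new flag programming and a few sparse tables. The dose dates needed are those already used for modal dose. A subject can appear in more than one dose column, so the columns will not add up to the number of subjects; a footnote should say so.
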